10.5 Exploratory Endpoints

1. Impact of ⁶⁸Ga-PSMA-11 PET on clinical management in patients with recurrence of prostate cancer.
2. Inter-reader reproducibility

10.6 Measurement Time Points

Uptake will be evaluated after the scan completion.

11. STATISTICAL CONSIDERATIONS

11.1 Statistical Design

Prospective single center, single-arm study. Patients will be scanned with ⁶⁸Ga-PSMA-11 PET/MRI. MRI and PET/MRI scans will each be evaluated separately by 3 readers.

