2.4 Rationale

In this study, we propose to use a well-established PET isotope, Gallium-68 (^{68}Ga), bound to a PSMA ligand, (ie, ^{68}Ga -PSMA-11), which has high affinity for prostate specific membrane antigen. ^{68}Ga -PSMA-11 has been shown to be superior to other PET tracers used in prostate cancer such as ^{18}F -Fluoroethylcholine (FECH) and ^{18}F -Fluoromethylcholine (31, 32). Therefore, we propose the following aim: to evaluate ^{68}Ga -PSMA-11 PET/CT for detection of recurrent prostate cancer after initial therapy in patients with elevated PSA.

A prior first-in-human study investigated the biodistribution of ^{68}Ga -PSMA-11 and its ability to detect lesions. Thirty-seven men with prostate cancer underwent whole-body PET/CT after an intravenous injection of ^{68}Ga -PSMA-11 (median 121.0 MBq, range 52–212 MBq). Within healthy organs, kidneys and salivary glands demonstrated the highest radiotracer uptake. Lesions suspicious for PC presented with excellent contrast as early as 1 hour post-injection with high detection rates even at low PSA levels (30). In another study, a total of 78 lesions characteristic for prostate cancer were detected in 32 patients using ^{68}Ga -PSMA-11 PET/CT and 56 lesions were detected in 26 patients using choline PET/CT (32). The higher detection rate in ^{68}Ga -PSMA-11 PET/CT was statistically significant ($P = 0.04$). All lesions detected by ^{18}F -fluoromethylcholine PET/CT were also seen by ^{68}Ga -PSMA-11 PET/CT. In conclusion, ^{68}Ga -PSMA-11 PET/CT can detect prostate cancer lesions with improved contrast when compared to ^{18}F -fluoromethylcholine PET/CT, especially at low PSA levels.

[figure not shown]

Figure 2: Red arrows point to a nodular pelvic wall metastasis (a, b, histologically-confirmed) and to small lymph nodes (c, d) which present with clearly pathological tracer uptake in ^{68}Ga -PSMA-11 PET/CT (b and d) only. Yellow arrows point to both catheterized ureters (c, d). Patient presented with a minimal PSA value (0.01 ng/mL) despite visible tumor lesions. The PSMA-11 ligand is therefore able to detect poorly differentiated PC. a + c Fusion of ^{18}F -fluoromethylcholine PET and CT; b + d fusion of ^{68}Ga -PSMA-11 PET and CT.

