10. MEASUREMENTS

10.1 Outcome Measures

The principal goal of this study is to compare, in the setting of suspected prostate cancer recurrence, the diagnostic performance of ^{68}Ga -PSMA-11 PET/CT in cases where conventional imaging for detecting recurrent prostate cancer is likely to have false negatives. Sites of suspected disease will be evaluated by ^{68}Ga -PSMA-11 PET/CT and conventional imaging by region for all patients. Specifically, it is hypothesized that the diagnostic performance of the ^{68}Ga -PSMA-11 PET/CT will be superior to anatomical imaging, and that ^{68}Ga -PSMA-11 PET/CT will provide complementary information.

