10.1.1 Primary Outcome

Primary Outcome Title: Confirmation of Prostate Cancer Recurrence

Description: Prostate cancer patients with suspected prostate cancer recurrence will be evaluated with ^{68}Ga -PSMA-11 PET/CT and conventional imaging. The outcome will be reported as the percentage of participants for whom tumor lesions are identified by ^{68}Ga -PSMA-11 PET/CT, and for whom tumor lesions are identified by histopathology/biopsy and/or conventional imaging follow-up. The outcome is reported as percentages without dispersion.

Time Frame: 1 year

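### The analysis population, the scan named in the design, the two primary outcomes and the superiority hypothesis do not fit the planned accuracy analysis

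*Combined protocol and SAP*

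**What the plan says.** **Population and analysis.** Section 11.3.1 defines the population as the lesions that PET/CT identifies. Section 11.3.2 then asks for point estimates and 95% confidence intervals for the percentage of patients with true lesions and for sensitivity and specificity. Synopsis hypothesis 2 sets both accuracy measures at 70% or more.

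**Scan.** Section 11.1 states "Patients will be scanned with" PSMA-11 PET/MRI, and continues: "MRI and PET/MRI scans will each be evaluated separately by 3 readers". The synopsis, 2.5, 5.1, 5.2 and 11.3 specify PET/CT.

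**Primary outcome.** Section 10.1.1 is headed "Primary Outcome Title: Confirmation of Prostate Cancer Recurrence". It reports percentages of participants with lesions identified by PET/CT and "for whom tumor lesions are identified by histopathology/biopsy and/or conventional imaging follow-up", with no measure of dispersion. Section 10.3 names the primary endpoint as sensitivity and PPV, per patient and per region, against histopathology/biopsy only.

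**Goal.** Section 10.1 says "The principal goal of this study is to compare, in the setting of suspected prostate cancer recurrence, the diagnostic performance of" PSMA-11 PET/CT, hypothesises that "PET/CT will be superior to anatomical imaging", and plans evaluation by "PET/CT and conventional imaging by region for all patients". Section 2.4 is more modest: "Therefore, we propose the following aim: to evaluate" PET/CT for detecting recurrence.

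**The concern.** Sensitivity needs diseased units that the test missed, and specificity needs disease-free units that it called negative. A population of PET-identified lesions supplies neither, so the second item of the analysis plan and synopsis hypothesis 2 cannot be answered from the set as written.

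The other conflicts leave choices open until the data are seen: which outcome is primary, which reference standard decides it, and whether a claim against conventional imaging will be made. The available text also does not say how patients without confirmation are scored. The 70% threshold could therefore be met or missed through the choice of reference rather than through the performance of the scan.

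**Working it through.** **1. The plan's own precision (11.4).** Half-width = 1.96 × √(p(1−p)/n).
- p = 0.30, n = 200: 1.96 × √(0.21/200) = 6.35 points; the exact interval is 23.7% to 36.9%. This agrees with roughly ±7.
- p = 0.70: n = 60 (30% of 200) gives ±11.6 points and n = 140 gives ±7.6. A half-width of 10 points needs 0.21 × (1.96/0.10)² ≈ 81 patients in the denominator. Roughly ±10 is plausible, though no denominator is stated.

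Both are single-sample figures. Neither sizes a comparison.

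**2. The 11.3.1 set, for one read.** Every unit is PET-positive, so FN = TN = 0.
- Sensitivity = TP/(TP + 0) = 100% by construction.
- Specificity = 0/(0 + FP) = 0%, or undefined if FP = 0.
- NPV = 0/0, undefined.
- PPV = TP/(TP + FP), estimable.

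**3. Sections side by side.**

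| Item | One place | Another place |
|---|---|---|
| Scan | 11.1: PET/MRI, plus separate MRI reads | Synopsis, 2.5, 5.1, 5.2, 11.3: PET/CT; the section 7 calendar lists no MRI |
| Primary measure | 10.1.1: percentage of participants | 10.3: sensitivity and PPV |
| Primary reference | 10.1.1: histopathology and/or imaging follow-up | 10.3: histopathology/biopsy only |
| Composite reference | 10.1.2: *and/or* | 10.4: *and* |
| Uncertainty | 10.1.1: no dispersion | 11.3.2: 95% CI |
| PPV | 10.3: half of the primary endpoint | 11.3.2: not listed |
| Hypothesis 1 and its paired analysis | Synopsis hypothesis: lesions detected | Synopsis analysis item 1: true lesions |

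Section 5.3 blinds readers to another scan without naming it, and describes three-reader interpretation for PSMA PET only.

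**4. Superiority.** Sections 10.1.1 to 10.5, 11.3.2 and 11.4 contain no difference, ratio or paired test against conventional imaging.

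**5. How far the reference can move sensitivity (illustration only).** The documents give no histology rate and no accuracy for imaging follow-up. Assumed inputs:
- PET sensitivity 70% (the synopsis threshold), 30% of men PET-positive (the planned discovery rate) and PET specificity 95%. Prevalence is then (0.30 − 0.05)/(0.70 − 0.05) = 0.385.
- Resulting cells: diseased PET+ 0.2692, disease-free PET+ 0.0308, diseased PET− 0.1154, disease-free PET− 0.5846.
- Imaging follow-up has sensitivity s = 25, 50 or 80% and specificity 95%, with errors independent of PET.
- Histology is error-free and decides where done. It is done in 50% of PET-positive men and a fraction f of PET-negative men, at the same rate in diseased and disease-free men.

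Histology only: sensitivity = 0.2692 × 0.5 / (0.2692 × 0.5 + 0.1154 × f).

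Composite: sensitivity = A/(A + B), where A = 0.2692 × (0.5 + 0.5s) + 0.0308 × 0.5 × 0.05 and B = 0.1154 × (f + (1 − f)s) + 0.5846 × (1 − f) × 0.05. For s = 0.25 and f = 0.05, A = 0.1690, B = 0.0609 and sensitivity = 73.5%.

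| f | Histology only | Composite, s = 25% | s = 50% | s = 80% |
|---|---|---|---|---|
| 5% | 96% | 74% | 70% | 67% |
| 10% | 92% | 73% | 69% | 67% |
| 20% | 85% | 71% | 69% | 67% |
| 50% | 70% | 66% | 67% | 67% |

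The gap between the two references runs from about 3 points (f = 50%) to about 29 points (f = 5%, s = 80%).

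**The case against.** The strongest reply is that most of this is loose drafting that nobody would implement literally. The outcomes in 10.1.2 are per participant and the sample size counts patients. Section 10.2 grades sites as positive or negative at two thresholds and 5.3 uses three readers, so a lesion identified on one read may be negative on another. The hypotheses labelled as such in the synopsis are single-arm, and 2.4 aims only to evaluate. The PET/MRI sentence looks carried over and changes no calculation. A histology tier with a composite tier beneath it is legitimate.

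Much of that stands, and it limits the point. A reader might infer that the 100% and 0% in step 2 hold unconditionally. They hold for a single read, and the 0% also needs at least one false positive. Even across reads, though, the set leaves out disease that every PET read missed, so 11.3.1 still has to change.

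Other stronger readings are tempting but unsupported:
- That sensitivity could be reported as low as 54%. That figure needs imaging follow-up alone as the reference (s = 25%), and no section defines such a reference.
- That the MRI read should simply be deleted. Section 10.1 plans conventional imaging for all patients, and the checklist title names MRI among the conventional methods, so this may be a remnant of the comparator read.
- That 10.1.1 already supplies the comparison. It may report two percentages side by side, or PET-positive men who are confirmed. Neither reading defines a contrast, and its second element is the reference standard.
- That hypothesis 1 is untouched. As worded it needs no reference standard, but the analysis item paired with it does.
- That the sample-size statement is wrong. It is about right for single-arm estimates.

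**Conclusion.** The point holds, as something that should be fixed. Four defects can be read directly from the text:
- an analysis population that supports PPV but not sensitivity or specificity;
- a design statement naming a scan that the trial does not acquire;
- two primaries that differ in measure and in reference standard;
- a superiority hypothesis with no matching analysis.

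The size of the reference-standard effect is not known from the documents. Under the stated assumptions a true sensitivity of 70% is reported as about 66-74% with the composite and 70-96% with histology alone, so the result can fall on either side of the 70% threshold. Much of that spread comes from the assumed verification rates and imaging accuracy as well as from the conflict in wording. If PET and follow-up imaging tend to miss the same disease, the composite figures would be higher. The range illustrates sensitivity to the choice; it does not predict the trial's result.

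**What to change.** - **11.3.1:** use all scanned patients for per-patient analyses and all their Table 1 regions for per-region analyses.
- **11.1:** replace PET/MRI with PET/CT read by three readers as in 5.3. Reconcile the MRI read with 10.1: remove it if no comparator read is intended, otherwise restate it as the conventional-imaging read.
- **10.1.1 and 10.3:** name one primary outcome with one reference standard. Histology primary with composite secondary is acceptable if stated. Report 10.1.1 with a 95% CI.
- **10.1.2 and 10.4:** use one wording for the composite reference.
- **11.3.2:** add PPV and NPV, and align the true-lesion item with synopsis hypothesis 1.
- **10.1:** remove the comparison and superiority wording. Alternatively, if comparator reads exist, add a paired per-patient difference in detection with a 95% CI, described as detection and without pre-specified power.
- **Checklist title and 3.1:** reconcile the title's condition of non-contributory imaging with the inclusion criteria, which do not list it. If it is an entry condition, a paired difference must not be presented as superiority. If it meant no conventional detections at entry, 6 PET-positive men of 200 would already give a McNemar p of 2 × 0.5⁶ = 0.031 through selection alone.
- **Unverified patients:** report verified-only accuracy with best-case and worst-case bounds.

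Most of this is wording. The bounds need a verification status recorded per patient and region, and they widen the reported ranges. As an assumed example, take 36 true positives, 4 false positives, 12 false negatives and 58 true negatives verified, with 20 PET-positive and 70 PET-negative men unverified. Verified-only sensitivity is 36/48 = 75%, with bounds 36/118 = 31% to 56/68 = 82%. Specificity is 58/62 = 94%, with bounds 58/82 = 71% to 128/132 = 97%. The paired option also means abstracting baseline imaging for up to 200 men; if only clinical reports exist, those reads are neither standardised nor blinded.

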11.2 Randomization

No randomization will be done.

11.3 Key variables

11.3.1 Analysis Population

All lesions identified by ⁶⁸Ga-PSMA-11 PET/CT.

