INVESTIGATIONAL PRODUCT	⁶⁸ Ga-PSMA-11; also known as: 
 • DFKZ-11 • HBED-CC PSMA • The “Heidelberg compound”
PRIMARY OBJECTIVE	To evaluate ⁶⁸ Ga-PSMA-11 PET/CT for detection of recurrent prostate cancer after initial therapy in patients with elevated PSA
SAMPLE SIZE	200 participants
GOALS	
Prospective single-center, single-arm study.
 
HYPOTHESES
 
 1. At least 30% of these patients will have one or more lesions detected on ⁶⁸Ga-PSMA-11 PET/CT. 2. ⁶⁸Ga-PSMA-11 PET/CT will have sensitivity and specificity of at least 70% in this context. 
STATISTICAL TEST
 
We will calculate point estimates and 95% confidence intervals for:
 
 1. Percentage of patients who had true lesions. 2. Sensitivity and specificity of ⁶⁸Ga-PSMA-11 PET/CT. 
STATISTICAL POWER AND SAMPLE SIZE
 
We expect to recruit 200 patients over the course of this trial. The number of lesions cannot be predicted at this time, however, if our expectation of a 30% discovery rate is correct, the resulting confidence interval would be roughly +/- 7 percentage points, and confidence intervals for specificity/sensitivity would be roughly +/- 10 percentage points.

SCHEMA

Eligible participant with prostate cancer

LIST OF ABBREVIATIONS AND DEFINITION OF TERMS

Ga-68; ^{68}Ga	Gallium-68
IRB	Institutional Review Board
IV	Intravenous
MRI	Magnetic resonance imaging
NPV	Negative predictive value
PPV	Positive predictive value
PET	Positron emission tomography
SUV	Standardized Uptake Value
PSMA	Prostate Specific Membrane Antigen

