All participants tolerated the procedure without immediate or delayed (up to 7 days) complaints or complications. The areas with the highest ⁶⁸Ga-PSMA-11 accumulation are the lacrimal gland (mean SUV_{max}: 9.3 \pm 3.3 [range: 4.6 to 14.9] and SUV_{mean}: 5.2 \pm 2.3 [range: 2.5 to 8.8]), the parotid gland (mean SUV_{max}: 14.2 \pm 2.6 [range: 9.9 to 19.1] and SUV_{mean}: 11.8 \pm 2.6 [range: 7.2 to 16.1]), the submandibular gland (mean SUV_{max}:

16.8 ± 3.3 [range: 12.3 to 22.7] and SUV_{mean} : 13.5 ± 2.9 [range: 9.8 to 18.1]), small intestine (mean SUV_{max} : 14.6 ± 4.6 [range: 8.2 to 23.4] and SUV_{mean} : 11.0 ± 3.9 [range: 5.6 to 18.5]), kidney (mean SUV_{max} : 35.1 ± 9.9 [range: 14.4 to 46.2] and SUV_{mean} : 25.8 ± 7.5 [range: 12.0 to 36.0]) and bladder (mean SUV_{max} : 35.0 ± 24.7 [range: 9.6 to 78.5] and SUV_{mean} : 26.5 ± 17.4 [range: 7.8 to 67.9]), while moderate uptake was noted in the sublingual gland (mean SUV_{max} : 5.0 ± 2.4 [range: 1.9 to 10.6] and SUV_{mean} : 3.3 ± 1.6 [range: 1.5 to 7.1]), liver (mean SUV_{max} : 6.0 ± 1.3 [range: 4.1 to 9.0] and SUV_{mean} : 4.1 ± 0.8 [range: 3.2 to 5.7]) and spleen (mean SUV_{max} : 8.0 ± 3.3 [range: 2.6 to 12.3] and SUV_{mean} : 6.4 ± 2.7 [range: 2.0 to 10.5]). Other tissues analyzed had low ^{68}Ga -PSMA-11 uptake, with SUV_{mean} of less than 1.7. There were no differences between the ^{68}Ga -PSMA-11 biodistribution at 45 minutes post-injection among the 10 participants (Figure 2). The pattern of ^{68}Ga -PSMA-11 uptake is similar to previous reports.

^{68}Ga -PSMA-11 uptake outside the expected physiologic biodistribution

There were 45 areas of high ^{68}Ga -PSMA-11 uptake that corresponded on the CT images to bone marrow ($n = 13$), retroperitoneal lymph nodes ($n = 12$), mediastinal lymph nodes ($n = 8$), pelvic lymph nodes ($n = 9$), seminal vesicle ($n = 2$), subclavian lymph node ($n = 1$).

[figure not shown]

Figure 1: Maximum intensity projection (MIP) images from 10 participants in the pilot study conducted at Stanford University.

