2.5 Study Design

This is a phase 2-3 study with a total of 200 participants with biochemically recurrent prostate cancer. Eligible participants will undergo baseline assessments at enrollment. Study participants will receive ⁶⁸Ga-PSMA-11 and undergo a PET/CT. All patients will first be seen by a Stanford Cancer Institute physician and then referred if appropriate on clinical grounds to Dr [name] or his colleagues for this study. The following steps will take place.

1. After signed the informed consent document, participants will be given a copy of the signed form.
2. Participant will be asked to drink 1 to 2 glasses of water before arrival at the clinic
3. Participants will be weighed and vital signs (heart rate, blood pressure, respiratory rate, pulse oxymetry) will be recorded
4. Study personnel (eg, technologist) will verify subject identify; radiopharmaceutical identity; dose; and administration route. Participant will be injected IV with 3 to 7 mCi of ⁶⁸Ga-PSMA-11
5. A dose of 20 mg of furosemide is recommended to be injected together with, shortly before, or after administration of the radiotracer in order to minimize PET scatter artifacts from excreted radiotracer accumulation in the kidney and urinary bladder that can occur with ⁶⁸Ga-PSMA-11. However, this is not needed if the scanner can reduce such artifacts during image reconstruction
6. Participant will void immediately prior to the scan
7. Approximately 50 to 100 minutes later, a low-dose CT will be obtained from vertex to mid-thighs; this will use 120 kV and dose modulation based on body habitus, ranging 10 to 105 mA. This will be followed by a static PET emission scan over the same area.
8. If participant agrees, immediately after first scan and without reinjecting ⁶⁸Ga-PSMA-11, a second PET/CT will be acquired to compare standard vs digital PET/CT. The CT will be done for attenuation correction only.
9. Vital signs (heart rate, blood pressure, respiratory rate, pulse oxymetry) will be recorded again at the completion of the study.
10. Participants be dismissed.
11. Participants will be contacted at 24 to 72 hours following the scan in order to capture potential late occurring Adverse Events.
12. Clinical follow-up of participant at 3 to 12 months following the scan in order to analyze secondary endpoints.

The ⁶⁸Ga-PSMA-11 PET/CT may be repeated at the completion of treatment to evaluate response to therapy, if requested by the treating physician.

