5.3 Details of processing/analysis

The lesions will be analyzed by Nuclear Medicine physicians blinded to the diagnosis and results of the other scan, in a randomized order to avoid bias. ^{68}Ga -PSMA-11 PET data will be interpreted by 3 different readers in a random order at separate reading sessions. Cross sectional imaging from the PET will be available for anatomic correlate.

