7. STUDY CALENDAR

	Pre-Study	Scan Date	24 - 48 Hours Post-Scan	3-12 Months Post-Scan	12 Months (End-of-Study)
Informed consent	X				
Demographics	X				
Medical history	X				
^{68}Ga -PSMA-11		X			
Follow-up Call to Participant			X		
Clinical Follow-up				X	
Data analysis					X

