11.3.2 Analysis Plan

We will calculate point estimates and 95% confidence intervals for:

1. Percentage of patients who had true lesions.
2. Sensitivity and specificity of ^{68}Ga -PSMA-11 PET/CT.

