11.4 Sample Size

We expect to recruit 200 patients over the course of this trial. The number of lesions cannot be predicted at this time, however, if our expectation of a 30% discovery rate is correct, the resulting confidence interval would be roughly ± 7 percentage points, and confidence intervals for specificity/sensitivity would be roughly ± 10 percentage points.

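### Section 11.3.1 restricts the analysis to PET-identified lesions, which contradicts the per-patient and per-region endpoints and, read literally, makes sensitivity, specificity and NPV impossible to assess

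*Combined protocol and SAP*

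**What the plan says.** Section 11.3.1 is a single line: "All lesions identified by ⁶⁸Ga-PSMA-11 PET/CT". No participant-level or region-level analysis set is defined anywhere else.

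Section 11.3.2, directly below, plans point estimates and 95% confidence intervals for "Percentage of patients who had true lesions" and for sensitivity and specificity. Section 11.4 states "We expect to recruit 200 patients over the course of this trial", says that the lesion count is not predictable, and gives precision of about 7 points around a 30% discovery rate and about 10 points for sensitivity and specificity. The second synopsis hypothesis is that "PET/CT will have sensitivity and specificity of at least 70% in this context".

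Two passages bear on what *identified* means. Section 5.3 says "PET data will be interpreted by 3 different readers in a random order at separate reading sessions". Section 10.2 has suspected metastatic sites graded positive or negative twice, once for a more sensitive and once for a more specific read. Neither says which read puts a lesion into the analysis population.

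**The concern.** The population is selected on a positive index test and counted in lesions. Sensitivity, specificity and NPV all need units that the index test called negative, and the endpoints need patients or regions as the unit.

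Two analysts working from this document could use different denominators and report different results, each citing a section. One who follows 11.3.1 cannot assess the second hypothesis, NPV, or the sensitivity half of the section 10.3 primary endpoint. The patient percentage and the PSA-stratified detection rates would also lose the PET-negative men, although the sample size rests on all 200.

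**Working it through.** **1. Units, side by side.**

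| Section | Unit or denominator |
|---|---|
| 11.3.1 Analysis Population | lesions found by PET/CT |
| 10.1 Outcome Measures | regions, in all patients |
| 10.1.1 Primary Outcome | percentage of participants |
| 10.1.2 Secondary Outcomes | sensitivity, specificity, PPV, NPV by participant and by region; detection rate per patient by PSA stratum |
| 10.3, 10.4 Endpoints | per patient and per region |
| 11.3.2 Analysis Plan | percentage of patients |
| 11.4 Sample Size | 200 patients |

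Only 11.3.1 uses PET-identified lesions as its unit.

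**2. The plan's own precision figure.** With 30% of 200 patients (60/200), the Wald half-width is 1.96 × √(0.30 × 0.70 / 200) = 6.35 points. The exact interval is 23.7% to 36.9%, a half-width of 6.56. Both agree with the stated figure of about 7, the exact one more closely. Section 11.4 therefore uses patients, as its wording says, and not the 11.3.1 population.

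**3. The 2×2 table under 11.3.1.** Take *identified* to mean positive on the read being scored. Section 10.1.2 supports this, because it defines NPV over participants whom PET/CT did not identify. Every unit in the set is then PET-positive, so FN = TN = 0:

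- sensitivity = TP/(TP + 0) = 100% if TP > 0
- specificity = 0/(0 + FP) = 0%, or 0/0 if FP = 0
- NPV = 0/(0 + 0), undefined
- PPV = TP/(TP + FP), estimable, but per lesion

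**4. What a lesion-level PPV counts.** For the pilot, section 2.1 reports "There were 45 areas of high" uptake in 10 men: 13 + 12 + 8 + 9 + 2 + 1 = 45, and 45/10 = 4.5 per man on average. A man with several lesions enters a lesion-level PPV several times.

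**5. Illustration at patient level.** Suppose the restriction is carried over as PET-positive men only. The documents give no true disease rate, so a range is shown. Sensitivity and specificity are assumed to be 70%, the hypothesised minimum, with n = 200.

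| True disease rate | TP | FN | FP | TN | PET-negative men dropped | Percentage with disease among PET-positive men | Gap (points) | Detection rate on all 200 |
|---|---|---|---|---|---|---|---|---|
| 30% | 42 | 18 | 42 | 98 | 116 | 42/84 = 50.0% | 20 | 84/200 = 42% |
| 50% | 70 | 30 | 30 | 70 | 100 | 70/100 = 70.0% | 20 | 100/200 = 50% |
| 70% | 98 | 42 | 18 | 42 | 84 | 98/116 = 84.5% | 14.5 | 116/200 = 58% |
| 90% | 126 | 54 | 6 | 14 | 68 | 126/132 = 95.5% | 5.5 | 132/200 = 66% |

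On the restricted set the detection rate is 100% in every row, by construction.

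**The case against.** The strongest reply is that the rest of the plan already implies the right denominator. It plans per-patient specificity, a percentage of patients and evaluation of all patients, so no sensible analyst would report a specificity of 0% and an undefined NPV. On this view the realistic risk is an ambiguous denominator, curable by wording. It is true that the extreme result is conditional on one reading. But the correct denominator is reached only by disregarding the one section headed Analysis Population.

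A second reply is that *identified* may cover any candidate site seen by any of three readers or on either visual read, which leaves some negatives in the set. It may, but men and regions negative on every read stay out, so sensitivity, specificity and NPV are still distorted.

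Two limits on the numbers stand. The patient-level gaps depend on converting a lesion set into PET-positive men, a set the plan does not define, and on assumed accuracy and disease rates. The pilot average may not carry over either: pilot PSA ran from 2.6 to 36.4, while this trial admits men from just above 0.2 ng/mL after prostatectomy. Neither limit touches the contradiction.

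**Conclusion.** The concern holds, and the section must be corrected before analysis. That 11.3.1 conflicts with the endpoints, the analysis plan and the sample size needs no assumption. That sensitivity, specificity and NPV cannot be assessed rests on one condition, that *identified* means positive on the scored read. This is the reading closest to the protocol's own usage. On the looser reading the measures can be computed but are distorted. PPV is not lost, but has the wrong unit. The gaps of 5.5 to 20 points show the possible scale under stated assumptions and do not predict this trial's results.

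**What to change.** Replace section 11.3.1 with text to this effect:

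> *Participant analysis set:* all participants who received the tracer and completed the PET/CT, PET-positive or PET-negative. This set is the denominator for the patient percentage and the PSA-stratified detection rates.
>
> *Regional analysis set:* all four Table 1 regions of each such participant, positive or negative. Each region is analysed separately; if regions are pooled, standard errors are clustered by patient.
>
> *Accuracy measures:* sensitivity, specificity, PPV and NPV are computed among participants or regions in these sets whose status is established within 12 months by the composite reference (biopsy or histopathology, and/or follow-up with conventional imaging), or by biopsy or histopathology for the section 10.3 endpoint as stated there. The number unverified is reported by PET result. A sensitivity analysis counts all unverified units as recurrence, then all as no recurrence.

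Three related matters need their own decisions and are not settled by this change: which read or consensus makes a unit PET-positive, the biopsy-only reference in 10.3, and the composite reference, which section 10.1.2 joins with and/or but section 10.4 with and.

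The change needs wording and a little analysis, with no new patients, visits or scans. Its price is wider accuracy estimates, because some PET-negative men may lack a reference result. Section 2.5 schedules "Clinical follow-up of participant at 3 to 12 months following the scan in order to analyze secondary endpoints", and the section 7 calendar lists "Clinical Follow-up" without an imaging visit. The ranges below show the possible effect. They use the 70% tables above and assume that all PET-positive men are verified and that PET-negative men are unverified at random; the unverified shares are also assumed.

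| Disease rate | PET-negative men unverified | Sensitivity (all recurrence to none) | Specificity (all recurrence to none) |
|---|---|---|---|
| 30% | 20% (23.2 men) | 42/79.6 = 52.8% to 42/56.4 = 74.5% | 78.4/120.4 = 65.1% to 101.6/143.6 = 70.8% |
| 30% | 50% (58 men) | 42/109 = 38.5% to 42/51 = 82.4% | 49/91 = 53.8% to 107/149 = 71.8% |
| 90% | 20% (13.6 men) | 126/182.8 = 68.9% to 126/169.2 = 74.5% | 11.2/17.2 = 65.1% to 24.8/30.8 = 80.5% |
| 90% | 50% (34 men) | 126/187 = 67.4% to 126/153 = 82.4% | 7/13 = 53.8% to 41/47 = 87.2% |

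With many men unverified, the 70% hypothesis may stay undecided, but the report would show that openly.
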